Prescription history will be collected. Participants will be asked to bring all inhaled medications to this visit. Their self-reported use of either albuterol or combination albuterol/ipratropium will also be documented.

mMRC

Dyspnea ratings will be collected using the Modified Medical Research Council (mMRC) dyspnea scale.

CRQ-SR

The participant will complete the CRQ-SR^{13, 14} (Appendix 1) to assess disease-related quality of life.

Pulmonary Function Tests

Spirometry will be performed at Visit 1. Participants must have an FEV₁ ≥ 30 to be eligible for participation. Site staff will document the number of hours since the participant's last use of bronchodilators.

Additionally, peak inspiratory flow (PIF) will be measured using In-Check inspiratory flow device. The highest of three attempts should be recorded.

Vital Signs

Heart rate, blood pressure and SpO₂ will be collected before 6MWT is performed.

6-Minute Walk Test

A 6MWT will be performed according to international guidelines.^{15, 16} Parameters measured during this test include total distance walked and Borg¹⁷⁻¹⁹ dyspnea scale pre- and post-test. SpO₂ will be continuously measured using a pulse oximeter.

Modified Borg Assessment

The modified Borg assessment (Appendix 2) will be performed before and after 6MWT.

Inclusion/Exclusion Criteria Review

Site staff will review inclusion/exclusion criteria to determine participant eligibility. Only eligible participants will be randomized.

Device Photograph

Participants will be asked to bring their current jet nebulizer system to the visit. Study staff will take a photograph of the compressor, handset, and associated labels, if available.

Randomization

Participants will be randomly assigned to either their current jet nebulizer or the InnoSpire Go device for the first 30 days of treatment.

Training Session

Participants randomized to InnoSpire Go in the first treatment arm will be trained on the use and cleaning of the device before being sent home. These participants will be asked to refrain from using their own jet nebulizer system during this 30-day period.

Visit 2 – Interim Visit:

Participants will be asked to return to the research center 15 days \pm 3 days after Visit 1.

Side Effects and Adverse Event Assessment

Participants will be asked about any side effects or adverse events (AEs) since the last visit.

Concomitant Medications

Participants will be asked about any changes in their medication since the last visit.

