CRQ-SR (Follow-Up)

Participants will complete the follow-up CRQ-SR (Appendix 3) to assess disease-related quality of life since the previous visit.

Nebulizer Satisfaction Assessment

Participant satisfaction with the device used in the first treatment arm will be assessed. See Appendix 4 for assessment details.

Visit 3 – Cross-over:

Participants will be asked to return to the research center within 30 days \pm 3 days after Visit 1. They will be instructed to bring the first assigned study device and their prescribed albuterol or combination albuterol/ipratropium medication for the demonstration.

CRQ-SR (Follow-Up)

Participants will complete the follow-up CRQ-SR to assess disease-related quality of life since the previous visit.

Concomitant Medications

Participants will be asked about any changes in their medication since the last visit.

Device Use Demonstration

Participants will be asked to assemble their device and administer their next scheduled dose in the clinic to demonstrate their use of the device before completing the 6MWT. Site staff will verify that the demonstration does not conflict with patient's prescribed

dosage. All demonstrations will be video recorded to provide information on nebulizer use in post-study analysis.

Nebulizer Weight

The nebulizer cup/reservoir alone will be weighed with the medication before device use and after device use to capture residual medication. This process will take place during video recording.

PIF

Peak inspiratory flow will be measured using the In-Check inspiratory flow device. The highest of three attempts should be recorded.

Vital Signs

Blood pressure and SpO₂ will be collected after nebulizer use but before 6MWT is performed. Heart rate will be collected before nebulizer use, after nebulizer use, immediately after and approximately 15 minutes after the 6MWT.

Modified Borg Assessment

The modified Borg assessment will be performed three times (i.e., before and after nebulizer use and after 6MWT). The post-nebulizer Borg assessment should be performed at least 15 minutes after the completion of the nebulizer treatment.

6-Minute Walk Test

A 6MWT will be performed after nebulizer has been used and all post-nebulizer assessments (i.e., vital signs and modified Borg) have been completed.

Nebulizer Satisfaction Assessment

Participant satisfaction with the device used in the first treatment arm will be assessed.

Training Session

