Participants randomized to InnoSpire Go in the second treatment arm will be trained on the use and cleaning of the device before being sent home. These participants will be asked to refrain from using their own jet nebulizer system during this 30-day period.

Visit 4 – Interim Visit:

Participants will be asked to return to the research center 15 days \pm 3 days after Visit 3. Participants will complete procedures outlined in Visit 2.

Visit 5 –Final Visit:

Participants will return to the clinical facility 30 days (\pm 3 days) after Visit 3 completion. They will be instructed to bring the second assigned study device and their prescribed albuterol or combination albuterol/ipratropium medication for the demonstration. Participants will complete the procedures outlined in Visit 3. Participants will need to return all study equipment at this visit.

Participants will be discharged from the study following completion of study procedures.

Consent for Participation

Consent forms describing in detail the study intervention, study procedures and risks will be given to the participant and written documentation of informed consent is required prior to starting intervention/administering study intervention.

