The study investigator will complete an SAE/Unanticipated Adverse Device Effect Form and submit to the study sponsor and to the reviewing IRB as soon as possible, but in no event later than 10 working days after the investigator first learns of the effect. The study sponsor is responsible for conducting an evaluation of an unanticipated adverse device effect and shall report the results of such evaluation to local regulatory authorities and to all reviewing IRBs and participating investigators within 10 working days after the sponsor first receives notice of the effect. Thereafter, the sponsor shall submit such additional reports concerning the effect to local regulatory authorities.

Device Deficiencies

All device deficiencies, use or user errors, and equipment failures will be documented. Use or User errors will be captured as part of the source documentation. Device deficiencies and equipment failures will be kept on a separate log. The serial numbers and type of deficiency/failure will be captured. Unanticipated device deficiencies that lead to SAE's will be reviewed with the principal investigator (PI) and reported to the IRB as required.

Statistical Methods

Determination of Sample Size

The study plans to randomize up to 25 participants with a goal of having 20 participants complete the study. The sample size is based on project timelines and budgetary constraints.

General Considerations

The primary analysis will include all randomized participants. Descriptive data tables will be provided for all variables of interest. Continuous data will be presented by mean, standard deviation, median, minimum, and maximum observation. Data will be presented in the untransformed and transformed format (if applicable) for each continuous variable. Categorical data will be presented as frequencies and percentages. All formal statistical analyses will be performed using either SAS® or SPSS® software. Significance tests will be conducted at a two-sided significance level of $p < 0.05$.

There are no statistical criteria for terminating the study. No sensitivity analysis will be completed, and any deviations to the original statistical plan will be noted in the analysis report.

Participant Disposition

Participant disposition, including the total number of participants enrolled, completed, early terminations and withdrawals, will be presented. A listing will be provided with the reasons for discontinuation.

Primary Analysis

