Continuous ratings that are collected at only one interval per device will be examined using either a paired t-test or the non-parametric Wilcoxon Signed-Ranks test, depending on the distribution of the paired differences. Mixed Models with repeated measures may be used for endpoints collected at multiple intervals per device.

Categorical ratings that are provided for each device will be analyzed using the McNemar test; if there are more than two levels for these ratings, they will need to be grouped into two levels for this analysis.

Categorical preference endpoints that are answered at the final visit (e.g., “Which device do you prefer?”) will be analyzed with a One-sample Binomial Test that compares the observed proportion to a 50/50 split.

Treatment Compliance and Missing Data

Any discontinued participants or protocol deviations will be tracked and reported in data listings. If a participant discontinues a device after the 15-day assessment, their ratings will be carried forward to the 30-day interval for the intent-to-treat analysis. This imputation will only be necessary for participants that complete at least the 15-day assessment for both devices. If a participant discontinues before providing ratings for both devices, they will be excluded from the analysis.

Safety Analysis

Safety evaluations will be performed by recording clinical adverse events at the time originally reported, and they will be followed at regular intervals until resolution, or until the study is completed, whichever comes first. Adverse events will be provided in data listings.

Interim Analysis

Preliminary results will be assessed after 10 participants complete the study, but the sample size will not be adjusted based on these interim outcomes.

Direct Access to Source Data/Documents

Only site clinical study staff and approved Philips staff working with the research will know the identity of the participants. All information recorded by the study team and provided for analysis will be given a study ID number. A unique source record will be created for each study participant.

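### The paired tests planned for the once-per-device exploratory endpoints ignore any Visit 3 to Visit 5 shift; a period term with blocked sequences is a cheap improvement

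*Combined protocol and SAP*

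**What the plan says.** Under Visit 1, Randomization, device order is random: "Participants will be randomly assigned to either their current jet nebulizer or the InnoSpire Go device" for the first of two 30-day periods. The text gives no allocation ratio or blocking.

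Statistical Methods, Primary Analysis, sets three relevant rules:

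- Measured once per device: "Continuous ratings that are collected at only one interval per device will be examined using either a paired t-test" or a Wilcoxon signed-ranks test. The choice depends only on how the paired differences are distributed.
- Measured more than once per device: "Mixed Models with repeated measures may be used for endpoints collected at multiple intervals per device". The model is optional and its terms are not listed.
- Preference asked at the final visit, which is the primary endpoint (question 8): such endpoints "will be analyzed with a One-sample Binomial Test that compares the observed proportion to a 50/50 split".

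In the Schedule of Events, the endpoints with a single on-device value per period are 6MWT distance, Borg changes, video timings (time in mouth, time to fill, time to sputter) and fluid nebulized. These values come from Visits 3 and 5. The Visit 3 text says "All demonstrations will be video recorded to provide information on nebulizer use in post-study analysis" and "A 6MWT will be performed after nebulizer has been used and all post-nebulizer assessments" are complete; for Visit 5, "Participants will complete the procedures outlined in Visit 3". CRQ-SR and the satisfaction items are collected twice per device.

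General Considerations adds: "No sensitivity analysis will be completed". Discontinued participants are not replaced (Withdrawal), and those without ratings for both devices are excluded (Treatment Compliance and Missing Data).

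**The concern.** In a two-period crossover, device and period can be separated because order is randomised. A plain paired test does not use that information. A Visit 3 to Visit 5 change unrelated to device adds to the difference (InnoSpire Go minus jet) in participants who use InnoSpire Go second and subtracts from it in those who use it first.

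With equal sequences the shift cancels from the mean but stays in the variance, which costs power. With unequal sequences part of it also stays in the mean. An uneven analysed split is realistic here: no blocking is stated, withdrawals are not replaced and incomplete participants drop out.

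A shift is possible but not established. The video timings and weights have no Visit 1 demonstration, so Visit 3 is the first recorded demonstration and Visit 5 the second. For 6MWT the Visit 1 walk makes a learning shift less likely. For CRQ-SR and satisfaction, period is neither included nor excluded, because the model is unspecified. With sensitivity analyses ruled out, no later step is planned that would show a shift.

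**Working it through.** **Inputs from the documents.** 20 completers as the goal, from up to 25 randomised; two-sided 0.05 (Statistical Methods). The sample size rests on timelines and budget, so there is no stated power or effect size to reproduce.

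**Assumptions, not in the documents.** n = 20 analysed. Paired differences D are normal with SD 1. The Visit 3 to Visit 5 shift π is 0, 0.25 or 0.5 SD of D. The device effect τ = 0.660 SD gives the paired t-test 80% power with no shift. No carryover.

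**Model.** D has mean τ + π in the n1 participants who use InnoSpire Go second and τ − π in the n2 who use it first.

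1. *Bias of the paired mean, given the split:* π(n1 − n2)/n. At π = 0.5 this is 0.5 × 6/20 = 0.15 SD at 13:7 and 0.5 × 8/20 = 0.20 SD at 14:6. At 10:10 it is 0.
2. *Variance inflation:* the sum of squares is noncentral chi-square with 19 df and noncentrality 4π²n1n2/n. The expected sample variance is therefore 1 + 4π²n1n2/[n(n − 1)]. At 10:10 this is 1 + 100/380 = 1.26 for π = 0.5 and 1 + 25/380 = 1.07 for π = 0.25.
3. *Period-adjusted test:* the average of the two sequence means of D, with standard error √[(1/n1 + 1/n2)/4] and 18 df. Neither its level nor its power depends on π.

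Numerical integration for the paired t-test and the noncentral t for the adjusted test give:

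| Split | Paired type I error, π = 0.25 | Paired type I error, π = 0.5 | Adjusted type I error | Adjusted power |
|---|---|---|---|---|
| 10:10 | 4.4% | 2.9% | 5.0% | 80% |
| 12:8 | 4.9% | 4.5% | 5.0% | 78% |
| 13:7 | 5.5% | 6.5% | 5.0% | 76% |
| 14:6 | 6.4% | 9.7% | 5.0% | 73% |

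Paired t power at 10:10 is 80% with no shift, 78% at π = 0.25 and 72% at π = 0.5. Simulation agrees with the t-test figures, and the Wilcoxon type I error is similar (6.0% at 13:7 and 9.3% at 14:6 for π = 0.5).

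**How often the split is uneven.** Simple randomisation of 20 gives 13:7 or worse with probability 26% and 14:6 or worse with 12%. If 25 are allocated 13:12 in blocks and five are lost at random, these become 1.5% and 0%.

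**Power averaged over splits.**

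| Allocation | π | Paired t | Adjusted |
|---|---|---|---|
| Simple | 0 | 80.0% | 77.5% |
| Simple | 0.25 | 77.6% | 77.5% |
| Simple | 0.5 | 70.7% | 77.5% |
| Blocked, random loss | 0 | 80.0% | 79.3% |
| Blocked, random loss | 0.25 | 78.0% | 79.3% |
| Blocked, random loss | 0.5 | 71.9% | 79.3% |

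Averaged over simple randomisation, paired t type I error is 5.0% at both shifts. Adjustment starts to gain power at a shift of 0.09 SD at 10:10, 0.15 SD under blocking and 0.25 SD under simple randomisation.

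**Question 8.** With 20 answers the exact test rejects at 5 or fewer, or 15 or more. If 70% chose whichever device came second, regardless of type, type I error would be 5.3% at 13:7 and 7.6% at 14:6, but 4.1% averaged over simple randomisation. At 10:10 there is no bias under the null, although power may change.

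**The case against.** The plan contains no error in the strict sense. Because order is randomised, the paired t-test is unbiased and keeps its 5% level over simple randomisation; the 6.5% and 9.7% figures combine the larger assumed shift with uneven splits. At 0.25 SD the rates are 5.5% and 6.4%. This stands, and it is why the point is minor.

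A shift may also be small. Participants have used a jet nebulizer for six months, InnoSpire Go users are trained, and each demonstration follows about 30 days on that device. Borg endpoints are within-visit changes, and sputter time and weight may depend mainly on the device. This is reasonable but does not exclude a shift, least of all in time to fill or time in mouth.

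The period term is cheap only with blocking. Under simple randomisation it loses 2.5 points with no shift and gains nothing at 0.25 SD. This stands, so the two changes belong together.

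The list may already be blocked. The text does not say so, and Figure 2 was not visible in the copy reviewed. If it is blocked, stating the method is enough.

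Finally, where the Wilcoxon is chosen, the remedy offers only a display by sequence. That is true: a rank-sum replacement would not help (75% against 76% power at 0.25 SD and 10:10; 66% against 78% at 14:6 with no shift).

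**Conclusion.** The concern holds, as a minor improvement. The planned tests remain valid on average, and with no shift nothing is lost by keeping them. If there is a shift, they give up precision and, in an uneven split, attribute part of it to the device. The loss at 10:10 is about 2 points of power at 0.25 SD and 8 points at 0.5 SD. The size rests on assumed shifts, an assumed 80% starting power and normal differences, none of which the documents supply. Only exploratory endpoints are affected by the paired tests. The primary test and the sample size are not called into question, and a period term does not address carryover.

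**What to change.** 1. Analyse the once-per-device continuous endpoints with device and period in the model; the two-sequence t-test on within-participant differences is equivalent. Include period in any mixed model used for CRQ-SR and satisfaction.
2. Randomise sequence 1:1 in permuted blocks and state this in the protocol. If the list is already fixed, state how it was generated. The period term can still be specified before analysis, but without blocking it gains power only above about 0.25 SD.
3. Keep the Wilcoxon where it is chosen and show the differences by sequence.
4. Keep the exact binomial test for question 8 and report preference counts by sequence beside it, as description.

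The cost is SAP wording and the randomisation list, with no new data or visits. If there is no shift, average power falls by 0.7 points under blocking with random loss (80.0% to 79.3%) and by 2.5 points under simple randomisation (80.0% to 77.5%).

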Up to 25 stable ambulatory COPD patients who are currently prescribed jet nebulizer albuterol treatment or albuterol/ipratropium bromide combination will be included in this study. The goal is to have 20 participants complete the study.

Figure 2

Schedule of Events

Procedures	Pre-Screening	Visit 1 (Day 1) Screening/Baseline	Visit 2 (15 days ± 3 days after Visit 1) Interim Visit	Visit 3 (Day 30 ± 3 days) Crossover	Visit 4 (15 days ± 3 days after Visit 3) Interim Visit	Visit 5 (30 days ± 3 days after Visit 3) Final Visit
Recruitment	X					
Informed Consent		X				
Inclusion/Exclusion Criteria Review		X				
Demographics		X				
Medical History		X				
Height and Weight		X				
Concomitant Medication		X	X	X	X	X
Device Photograph		X				
Modified Medical Research Council Dyspnea Scale		X				
Chronic Respiratory Disease Questionnaire Self-Report		X	X	X	X	X
Spirometry		X				
Peak Inspiratory Flow Assessment		X		X		X
Vital Signs		X		X		X
6-Minute Walk Test		X		X		X
Modified Borg Assessment*		X		X		X
Device Use Demonstration (Audio/Video)				X		X
Nebulizer Weight				X		X
Training Session		X†		X§		
Side Effects and Adverse Event Assessment			X	X	X	X
Nebulizer Satisfaction Assessment			X	X	X	X

*Borg assessment will be performed up to three times at each designated visit (see visit procedures below).

†For participants randomized to InnoSpire Go in the first treatment arm.

§For participants randomized to InnoSpire Go in the second treatment arm.

Screening Procedures:

Participants will be contacted by designated study site staff. Participants may be pre-screened through medical records over the phone to assess potential eligibility. Participants that are interested will be scheduled for a screening visit at the clinical office.

Visit 1 – Screening/Baseline:

Once the participant arrives, the study will be explained in full detail. If the participant agrees, he/she will be consented into the study and the participant will be given a copy of the informed consent. After the consent is signed, the following procedures will be performed:

Demographics

Demographic data will be collected from standard sources.

Medical History

Information related to the patient's medical history, including COPD history.

Height and Weight

Participants' height and weight will be collected.

Concomitant Medication

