If a participant requests to stop using the device it does not mean discontinuation from the study, and remaining study procedures should be completed as indicated by the study protocol unless the participant does not wish to return and complete the follow-up visits. If a clinically significant side effect is identified (including, but not limited to negative changes from baseline) after enrollment, the investigator or qualified designee will determine if any change in participant management is needed. Any new any unfavorable and unintended sign (including an abnormal laboratory finding), symptom, or disease temporally associated with the use of the investigational device, whether or not related to the investigational device will be reported as an AE. See Assessment of Safety section for additional definitions and AE management.

Treatment of Subjects

Intended Use

InnoSpire Go is intended to be used as a general purpose mesh nebulizer used to aerosolize commonly prescribed liquid inhalation drugs for respiratory disease in children and adults. It is to be used by, but not limited to, patients with asthma, COPD and cystic fibrosis.

Contraindications

InnoSpire Go is not be used by patients that are unconscious or not breathing spontaneously.

Monitoring

Remote monitoring will be conducted for this study. Data that is directly entered into EDC will not be verified. 100% of the remaining data will be verified among 10% of the study participants' records.

This study will be monitored in compliance with Code of Federal Regulations (CFR) for clinical research; namely, 21 CFR Parts 50, 54, 56 and 812 and others as applicable. The purpose of such monitoring is to ensure that the rights and wellbeing of trial participants are protected, that the reported trial data are accurate, complete, and verifiable, and that the conduct of the trial is in compliance with the currently approved protocol/amendment(s), with International Conference on Harmonisation (ICH) Good Clinical Practice (GCP), and with applicable regulatory requirement(s). Monitoring visits will be performed periodically and will be conduct by trained clinical research

professionals. The monitoring process includes initial subject qualifications, periodic contact with the subject, and a final review once the study is complete.

It has been determined that this study does not require a Data Safety Monitoring Board (DSMB).

Unscheduled Visits

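### Carry-forward is triggered by stopping a device, not by a missing day-30 rating; read literally, it usually overwrites an observed rating for first-device stoppers

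*Combined protocol and SAP*

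**What the plan says.** The rule is in Statistical Methods, Treatment Compliance and Missing Data: "If a participant discontinues a device after the 15-day assessment, their ratings will be carried forward to the 30-day interval for the intent-to-treat analysis". The next sentence limits it: "This imputation will only be necessary for participants that complete at least the 15-day assessment for both devices". Participants without ratings on both devices are excluded.

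The section Discontinuation of Study Intervention separates stopping a device from leaving the study: "If a participant requests to stop using the device it does not mean discontinuation from the study, and remaining study procedures should be completed", with the exception "unless the participant does not wish to return and complete the follow-up visits".

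The first device's day-30 ratings are taken at Visit 3. Under the Visit 3 procedures, "Participants will complete the follow-up CRQ-SR to assess disease-related quality of life since the previous visit", and for the Nebulizer Satisfaction Assessment, "Participant satisfaction with the device used in the first treatment arm will be assessed". The Schedule of Events dates the second device's day-15 visit from Visit 3: "Visit 4 (15 days ± 3 days after Visit 3) Interim Visit".

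General Considerations rules out any sensitivity analysis.

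**The concern.** The protocol asks people who stop a device to keep attending and to give their ratings. The analysis section then tells the analyst, on its face, to use the day-15 value for them whether or not a day-30 value exists. An intent-to-treat analysis would normally keep an outcome observed after stopping.

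The direction matters. Someone who gives up a device late in its month may well rate it lower at day 30 than at day 15. Replacing the later rating with the earlier one removes the unfavourable observation and favours the stopped device. With a target of 20 completers, a few participants can move a mean. Two analysts reading the same sentence could also build different day-30 data sets, and no planned analysis would reveal the difference.

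**Working it through.** **Which ratings the rule can touch.** A day-15 value must exist. By the Schedule of Events, CRQ-SR and the Nebulizer Satisfaction Assessment are collected at Visits 2 to 5, so CRQ-SR and questions 1 to 7 are in scope. Question 8 (the primary endpoint) is asked only at Visit 5, per Appendix 4. The 6MWT and Borg are not done at Visits 2 or 4. None of these three has a day-15 value to carry.

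**What the rule does to a qualifying participant.** Qualifying means having ratings from Visits 2 and 4. With visits completed in order:

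| Device stopped after day 15 | Day-30 rating for that device | Rule as written | Trigger on a missing rating |
|---|---|---|---|
| First | Taken at Visit 3, before Visit 4 | Observed value replaced | Observed value kept |
| Second, attends Visit 5 | Taken at Visit 5 | Observed value replaced | Observed value kept |
| Second, misses Visit 5 | Missing | Gap filled | Gap filled |

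The first row is the main point. To qualify, the participant must reach Visit 4, which is timed from Visit 3, and Visit 3 is where the first device's day-30 ratings are given. The exception is a form or item left blank at Visit 3 by someone who went on to Visit 4; there the rule does fill a gap.

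**Size under the literal reading.** The plan has no figure to reproduce: the sample size rests on timelines and budget, and no stopping rate, fall or standard deviation is given. The stopper counts and falls below are therefore assumptions. The n values are the plan's goal of 20 completers and its maximum of 25 randomized.

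If k participants stop device A and their ratings fall by f points between day 15 and day 30, carrying day 15 forward raises each one's day-30 rating of A by f. With stoppers on both devices:

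shift toward A = (kA × fA − kB × fB) / n

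All stoppers on one device, 0-10 item:

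| k | f = 2, n = 20 | f = 4, n = 20 | f = 2, n = 25 | f = 4, n = 25 |
|---|---|---|---|---|
| 1 | 2/20 = 0.1 | 4/20 = 0.2 | 2/25 = 0.08 | 4/25 = 0.16 |
| 2 | 4/20 = 0.2 | 8/20 = 0.4 | 4/25 = 0.16 | 8/25 = 0.32 |
| 3 | 6/20 = 0.3 | 12/20 = 0.6 | 6/25 = 0.24 | 12/25 = 0.48 |

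A 2:1 split across devices at n = 20 gives (2 − 1) × 2/20 = 0.1 or (2 − 1) × 4/20 = 0.2. A 1:1 split with equal falls gives 0, as does f = 0. No size is given for CRQ-SR because its scale is not in the documents.

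**What changing the trigger removes (n = 20, all stoppers on the same device).**
- One first-device stopper: 0.1 becomes 0 (f = 2); 0.2 becomes 0 (f = 4).
- One stopper in each period, the second absent from Visit 5: 2 × 2/20 = 0.2 becomes 1 × 2/20 = 0.1; for f = 4, 0.4 becomes 0.2.
- Two in period 1 and one absent in period 2: 0.3 becomes 0.1; for f = 4, 0.6 becomes 0.2.

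What remains comes from ratings that are truly missing.

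**The case against.** The strongest reply is that the harm needs the less natural reading. The sentence sits under a heading that names missing data, and the next sentence calls the step an imputation. Imputation fills gaps, and nowhere does the plan say that an observed day-30 rating is to be discarded. On that reading the rule serves second-device stoppers who miss Visit 5 and is idle for first-device stoppers who were rated. Every shift from first-device stoppers is then zero. This stands as the likely intent, but the operative sentence does not contain the condition that the intent requires, and the protocol expects stoppers to supply day-30 ratings.

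It could also be said that discontinuing a device here means leaving the study, which is how the Withdrawal section uses discontinuation. The section on stopping the intervention separates the two. Moreover, someone who left the study during the first device would not reach Visit 4 and could not qualify.

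A third reply is that a rating given after stopping does not describe 30 days of use, so the day-15 value is the last one known to be on the device. This is a fair argument for a different target, but it does not fit the intent-to-treat label. The choice belongs to the sponsor and should be written down.

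A reader might go further than the documents allow in three ways.
- That the rule can never fill a first-device gap. A blank form or item at Visit 3 is an exception.
- That the trial's main result is biased. Question 8 has no day-15 value, so the rule cannot reach it.
- That the false-positive rate is inflated by a known amount. A paired t-test calculation would not settle this, because the plan assigns that test or the Wilcoxon test to ratings taken once per device. For ratings taken more than once it says only "Mixed Models with repeated measures may be used for endpoints collected at multiple intervals per device". No rejection rate is claimed here.

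**Conclusion.** The point holds as a wording defect with a possible bias of limited reach. As written, the trigger is stopping a device. Followed literally, the rule usually replaces an observed day-30 rating for a qualifying first-device stopper, and also for a second-device stopper who attends Visit 5. The visit-order argument rests on the schedule alone and assumes only that the Visit 3 forms were completed.

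The range of 0.1 to 0.6 points at n = 20 (0.08 to 0.48 at n = 25) is an illustration. It requires the literal reading, 1 to 3 stoppers all on one device, and a 2- to 4-point fall after day 15. If the analyst fills gaps only, first-device stoppers with a Visit 3 rating contribute no shift. The documents do not show that observed ratings will in fact be discarded, only that the text permits it. The change is worth making because it is cheap, but nothing in the primary analysis depends on it.

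**What to change.** In Treatment Compliance and Missing Data, replace the trigger with: *If the day-30 rating for a device is missing because the participant stopped that device after the 15-day assessment, the 15-day rating will be carried forward.* Then add: *Day-30 ratings collected after a device is stopped are analysed as observed in the intent-to-treat analysis.*

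The cost is one clause and one sentence, with no new data, visits or analyses.

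The downside is one of interpretation. A CRQ-SR completed after stopping looks back to the previous visit and so partly reflects time off the device, whereas the endpoint is worded in terms of 30 days of use. The added sentence makes the assigned-device (intent-to-treat) target explicit. A sponsor who wants an on-device target should say so instead.

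Two limits remain. The change does not help second-device stoppers who miss Visit 5: their day-15 value is still carried forward, and any unobserved fall still biases the comparison. It also leaves no rule for a participant who kept using a device but lacks its day-30 rating.
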